### 2.3.3 Summary

While the above-mentioned scoring systems and general clinical presentation of a patient are considered, approximately one third of all endoscopic interventions for suspected UGIB are inconclusive. This is deemed acceptable as patient risks from endoscopy are known and rare. Conducting an endoscopy on a patient that does not require one is considered safer than potentially missing a patient who would have needed endoscopic work up. HemoPill is designed to provide information on the acute presence or absence of blood/hematin in the gastrointestinal lumen. This piece of information has been shown to be valuable in the further risk stratification in patients with suspected UGIB. As described by Brunk T et al., a negative HemoPill measurement influenced the further clinical course of patients in 72 % of cases, mostly by shifting from emergency/urgent endoscopy to elective endoscopy. All HemoPill negative patients who did receive endoscopic work up did not show bleeding stigmata. The proposed clinical value of the HemoPill is that allocation of endoscopic resources can be more adequately planned which is a considerable financial benefit to the patient as well as the health care system. That being said, HemoPill is not intended to replace endoscopic procedures. Endoscopy does require patient preparation but has ultimately various curative possibilities in case pathologies are found. HemoPill solely provides information on the acute presence of blood/hematin in an otherwise unprepared patient in a real time fashion – no more, no less. The reliability of the measurement could already be shown in real-world use of the subject device in the EU. The value of the information on the presence or absence of blood/hematin in the GI lumen needs to be assessed within the context of the broader clinical presentation of a given patient and thus may differ from case to case.

**Hypothesis:**

Relation between HemoPill measurements to subsequent endoscopic findings show an adequate sensitivity and specificity for the HemoPill measurement regarding presence or absence of blood in the GI lumen.

**Justification for route of administration and selection of study population:**

Only patients already scheduled for an endoscopy on the basis of suspected UGIB are eligible for trial participation. HemoPill ingestion is embedded into the already fixed schedule for endoscopy. Endoscopy is not delayed by trial participation. HemoPill measurements do not influence the clinical course of a trial participant. Thus, no risks from false (e.g., false negative or false positive) measurements arise.

**Rational for endoscopy as a control measure:**

While there are differences between the function principle of the HemoPill and endoscopy, endoscopy is the most suitable control measure. UGIBs are volatile events as activity of a bleeding can be spontaneous. HemoPill is able to detect fresh blood and hematin within the GI lumen, thus solely requires presence of blood or hematin which can stem from a currently inactive pathology.

Endoscopy is able to identify blood or hematin as well as associated pathologies. Thus, relation between a HemoPill measurement and endoscopic findings is generally possible. Even more so if latency between HemoPill ingestion and endoscopy is a controlled parameter.

The aim of this clinical trial is to further investigate HemoPill's capacity to determine presence or absence of blood/hematin in a clinical setting by comparing a HemoPill measurement with endoscopic findings. Patients eligible for trial participation are already scheduled for endoscopy for suspicion of UGIB. Thus, the HemoPill measurement is not considered for further risk stratification and only put in relation to endoscopic findings after the fact. To allow for a reasonable comparison of HemoPill measurement and endoscopic findings, latency between the two is controlled. However, as scheduling for endoscopy is already in place as a prerequisite for trial participation, planning of HemoPill ingestion is embedded into endoscopy schedule – thus, no delay to endoscopy is introduced. The patient always receives endoscopy as planned, regardless of trial participation.

## **2.4 Potential Risks & Benefits**

### **2.4.1 Known Potential Risks**

As the subject device is already marketed in the EU, foreseeable risks and complications provided in the instructions for use are:

- Aspiration of the capsule on ingestion
- Delayed excretion, or failure to excrete the capsule (capsule retention)
- Obstruction of the digestive tract
- Injury to tissue structures during the passage of the HemoPill acute through the digestive tract. In particular:
  - o Injury to the mucosa
  - o Bleeding, e.g., variceal bleeding
  - o Perforations

The above-mentioned risks are generally associated with capsule endoscopy. So far, no case of harm to a patient from the use of the HemoPill has been reported.

### **Risks to participants by virtue or trial participation**

- Immediate risks
  - o Aspiration of the capsule on ingestion
  - o Obstruction of the digestive tract
  - o Injury to tissue structures during the passage of the HemoPill acute through the digestive tract. In particular:
    - Injury to the mucosa
    - Bleeding, e.g., variceal bleeding
    - Perforations
- Long-range risks
  - o Obstruction of the digestive tract
  - o Delayed excretion, or failure to excrete the capsule (capsule retention)

- Necessity of exposing human participants to above-mentioned risks

The above-mentioned risks are generally associated with capsule endoscopy, e.g., video capsule endoscopy. As of today, no incidence of patient harm from use of HemoPill has been reported. Within the trial context, HemoPill is ingested in a closely supervised setting. Within the trial context, a HemoPill measurement does not influence the clinical course of a given trial participant. Thus, any hypothetical risks from false negative or false positive measurements are avoided.

On the other hand, investigating HemoPill's capacity for reliably providing information on the presence or absence of blood in the GI lumen has the potential to better understand the clinical applicability of the device and provide information on the proposed clinical benefit. In case HemoPill shows to be a reliable and effective tool, it can be safely introduced into clinical routine and unfold its then identified potential.

- Value of the information to be gained outweighs the risks involved

So far, HemoPill use has not resulted in any harm to a patient. The known risks are controllable and generally associated with capsule endoscopy. A risk from a potential false negative or false positive measurement does not apply within the context of the trial as the HemoPill measurement is disregarded in patient assessment. The value of a side-by-side comparison to endoscopy however further distinguishes the performance profile of the subject device. Scientifically sound determination of accuracy parameters is achievable with the proposed trial design. With these accuracy parameters adequately determined, the use of the HemoPill (once legally marketed) as well as interpretation of HemoPill measurement is tremendously facilitated. Introducing HemoPill into the clinical routine for risk stratification of suspected UGIB patients facilitates adequate allocation of emergency resources and potentially avoids unnecessary endoscopies altogether, as Brunk T. et al have shown.

- Rationale: Exclusion of alternative procedures

HemoPill is compared to an endoscopy already scheduled regardless of trial participation. Ultimate goal of the trial is establishing accuracy parameters of the HemoPill measurement to provide data needed for an adequate risk evaluation. The HemoPill measurement is however disregarded for further patient evaluation. Thus, no alternative procedure is required as it would also not influence the further clinical course of a trial participant. The control method endoscopy is already indicated and scheduled as per NYU protocol and neither delayed nor prolonged by trial participation.

## 2.4.2 Known Potential Benefits

With regard to trial participation, no immediate potential benefits are expected for a trial participant. Long range potential benefits stem from an introduction of HemoPill into the US market. On the basis of then established accuracy parameters, adequate consideration of HemoPill measurements for risk stratification will potentially lead to avoidance of endoscopic procedures if overall clinical presentation permits, which is a considerable benefit to a patient. Improving risk stratification precision by taking HemoPill measurements into consideration introduces benefits the health care system in general as decision for urgent or elective endoscopies are made on the basis of additional relevant and previously unavailable information on the presence or absence of blood/hematin in the GI lumen.

HemoPill is designed to provide information on the presence or absence of blood or hematin in the gastrointestinal lumen. The measurement data is depicted graphically and numerically in real time and allows for immediate data evaluation based on the introduced measurement value threshold. Ingestion of the HemoPill acute capsule does not require patient preparation and usability testing as well as clinical use in Europe indicates easy use and data assessment. The information on the presence or absence of blood in suspected UGIB patients is usually only available from nasogastric tube aspiration. However, this procedure has major deficiencies and is associated with a mediocre sensitivity and specificity as well as discomfort to the patient. HemoPill acute ingestion on the other hand has not caused any such discomfort. The value of the information on presence or absence of blood or hematin in a patient with suspected UGIB has to be assessed within the context of the overall clinical presentation of said patient, e.g., scoring systems, blood samples, Hb value, blood pressure etc.

The real-world clinical benefit from HemoPill use is best described by Brunk T et al (see chapter 2.1). Here, a negative HemoPill measurement influenced the further clinical course of patients in 72 %: 40 % of patients were rescheduled from urgent to elective endoscopy, in 20 %, small bowel enteroscopy could be avoided and in 12 %, EGD could be avoided. No HemoPill negative patient has a clinically significant bleeding until discharge. In HemoPill positive patients, median time to EGD was 3 h 18 minutes (range: 12 min – 64 h 52 min), whereas median time to EGD (if performed) was 19 h 52 min (range: 1 h 45 min – 146 h 10 min), which beautifully presents the influence of a HemoPill measurement within the broader context of risk stratification in patients with suspected UGIB.

Further benefits from availability of the HemoPill were reported within the context of risk stratification under COVID-19 pandemic conditions. Elsayed I et al. report on three cases as described in chapter 2.1. The authors conclude that the sensor capsule might aid in decision-making during the COVID-19 pandemic. In patients with as yet unavailable COVID-19 test results, HemoPill might aid in determining the appropriate time for endoscopy. In patients who are positive for COVID-19 with suspected UGIB, HemoPill could help on deciding whether to perform an endoscopy or not and thereby help minimizing risk of disease transmission.

## 3 Objectives and Purpose

### 3.1 Primary Objective

The objective of the study is to determine the clinical relation between the detection of blood in the GI lumen using the HemoPill acute (trial procedure) with the detection of bleeding / a bleeding source during an endoscopic examination (control procedure). The study is an intra-case control procedure.

## 4 Study Design and Endpoints

### 4.1 Description of Study Design

Patients are included according to the defined inclusion criteria and prepared for endoscopy. At the latest possible time before endoscopy, a HemoPill acute capsule is administered with a minimal amount of water. The HemoPill receiver is stored in a carrying bag. The transparent part of the bag over the display of the receiver is covered with tape. The LED light is left uncovered, so a successful signal transmission can be checked at any times. The investigator is unaware of the HemoPill acute measurement result until endoscopy has concluded. After a latency of minimum 20 minutes, maximum 60 minutes, endoscopy is performed as scheduled, identifying blood within the GI lumen, if present. A minimum latency is introduced to ensure HemoPill acute is able to make a measurement without interference from endoscopy, e.g., insufflation or endoscopic light.

The amount of blood identified in endoscopy is visually analyzed and pictures are taken. For the estimation of the amount of blood present in a patient, comparative images are provided. Assessment categories are:  $x < 20$  mL and  $x > 20$  mL. The detection threshold is introduced to provide a point of reference for the HemoPill acute detection rate.

Pathologies, if found, are treated as per clinical standard. HemoPill acute measurements regarding presence or absence of blood are put in relation to endoscopic findings.

Endoscopic images are further analyzed to determine the digestive state of the blood found as HemoPill acute is capable of detecting fresh blood or hematin. Blood digested to a point beyond hematin is no indicator for an acute bleeding pathology. The following foreseeable combination of events are described and allocated to “True Positive”, “False Positive”, “True Negative”, and “False Negative”.

- **True positive:**  
HemoPill acute measurement indicates presence of blood; Endoscopy identifies fresh blood or hematin in the GI lumen
- **False positive:**  
HemoPill acute measurement indicates presence of blood; Endoscopy does not identify fresh blood or hematin in the GI lumen.
- **True negative:**  
HemoPill acute measurement does not indicate presence of blood; Endoscopy does not identify fresh blood or hematin in the GI lumen in quantities  $> 20$  mL; Minimum latency of 20 minutes achieved.
- **False negative:**  
HemoPill acute measurement does not indicate presence of blood in the GI lumen; Endoscopy identifies fresh blood or hematin in the GI lumen in quantities  $> 20$  mL; minimum latency of 20 minutes achieved.

Patient recruitment goal is set at 50 patients as derived from statistical planning, including potential dropouts. The proposed clinical trial is a single-arm, single-center clinical trial. The control procedure endoscopy is applied in all trial participants as an intra-case relation of HemoPill measurement and endoscopic evaluation is performed.

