True Positive	HemoPill acute measurement indicates presence of blood; Endoscopy identifies fresh blood or hematin in the GI lumen.		

	True Negative	HemoPill acute measurement does not indicate presence of blood; Endoscopy does not identify fresh blood or hematin in the GI lumen in quantities > 20 mL; Minimum latency of 20 minutes achieved.
	False Positive	HemoPill acute measurement indicates presence of blood; Endoscopy does not identify fresh blood or hematin in the GI lumen.
	False Negative	HemoPill acute measurement does not indicate presence of blood in the GI lumen; Endoscopy identifies fresh blood or hematin in the GI lumen in quantities > 20 mL; Minimum latency of 20 minutes achieved.

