## 4.2 Study Endpoints

### 4.2.1 Primary Study Endpoints

Clinical effectiveness endpoint

- Result Accuracy: Clinical relation between HemoPill acute measurement (trial procedure) and endoscopic findings (control procedure) according to the defined scenarios for “true positive”, “false positive”, “true negative”, “false negative” (see above, chapter 4.1).

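### The capsule result selects the endoscopic cut-off, so a patient with fresh blood or hematin not above 20 mL can never count as an error, and accuracy, sensitivity and specificity can be inflated

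*Combined protocol and SAP*

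**What the plan says.** Section 4.1 and the synopsis give the same four definitions:

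- True positive: "HemoPill acute measurement indicates presence of blood; Endoscopy identifies fresh blood or hematin in the GI lumen".
- False positive: capsule positive and "Endoscopy does not identify fresh blood or hematin in the GI lumen".
- True negative: capsule negative and "Endoscopy does not identify fresh blood or hematin in the GI lumen in quantities > 20 mL; Minimum latency of 20 minutes achieved".
- False negative: capsule negative and "Endoscopy identifies fresh blood or hematin in the GI lumen in quantities > 20 mL; Minimum latency of 20 minutes achieved".

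The 20 mL limit appears only in the two capsule-negative cells. Section 4.1 explains it in one sentence: "The detection threshold is introduced to provide a point of reference for the HemoPill acute detection rate". Blood that is digested further is dealt with separately ("Blood digested to a point beyond hematin is no indicator for an acute bleeding pathology") and is not part of this point.

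Section 4.2.1 makes these cells the primary endpoint: "Clinical relation between HemoPill acute measurement (trial procedure) and endoscopic findings (control procedure) according to the defined scenarios for" the four outcomes. Section 10.4.2 computes accuracy, sensitivity and specificity from them. It treats endoscopy as a single positive or negative result, states no cut-off, and refers back to 4.1. Section 10.4.1 assigns case or control status from endoscopy alone. There is no separate SAP (10.1) and no subgroup or exploratory analysis (10.4.8, 10.4.9.2). Nowhere is one cut-off applied to all four cells.

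**The concern.** A diagnostic accuracy table needs a reference status that is fixed without knowledge of the index test. Here the status of a small-volume patient depends on the capsule: diseased if it reads positive, not diseased if it reads negative. If small volumes count as blood, a negative reading should be a false negative. If they do not, a positive reading should be a false positive. The definitions take the favourable answer each time.

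The primary result is at stake. Section 10.2 tests accuracy against 50%, which it equates with no relation between the two measurements. If small-volume patients are always scored correct, a capsule with no relation to blood can exceed 50%, and a significant result may partly reflect the scoring rule. The plan also contradicts itself, because the single endoscopy status of 10.4.1 and 10.4.2 cannot be formed for these patients under 4.1.

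**Working it through.** **1. The plan's own figure.** Section 10.2 gives accuracy 50% (null) against 75%; section 10.5 gives alpha 0.05, power at least 90% and n = 43. Reading the test as correct against incorrect, w = sqrt(0.25²/0.5 + 0.25²/0.5) = 0.50. With 1 degree of freedom and n = 43 the power is 90.6%, so 43 is reproduced. The printed w = 0.62 instead matches the four counts 20/15/25/0 of 60 from the multicentre study in 2.1, set against 25% each (0.624). The test wording is therefore ambiguous. The figures below assume correct against incorrect.

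**2. Scoring under each rule** (20-minute latency met).

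| Endoscopy | Capsule | As written | Any blood | >20 mL |
|---|---|---|---|---|
| None | + | FP | FP | FP |
| None | − | TN | TN | TN |
| Not above 20 mL | + | TP | TP | **FP** |
| Not above 20 mL | − | TN | **FN** | TN |
| Above 20 mL | + | TP | TP | TP |
| Above 20 mL | − | FN | FN | FN |

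**3. Direction.** Let Z, S and L be patients with no, small and >20 mL blood, with + or − for the capsule.

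- Sensitivity as written = (L+ + S+)/(L+ + S+ + L−). The >20 mL version drops S+ from top and bottom; the any-blood version adds S− to the bottom.
- Specificity as written = (Z− + S−)/(Z− + S− + Z+). The >20 mL version adds S+ to the bottom; the any-blood version drops S− from top and bottom.

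Neither index is ever lower as written. With t the small-volume share and q the capsule-positive rate within it, accuracy as written exceeds the >20 mL value by t·q and the any-blood value by t·(1−q). The two excesses sum to t.

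**4. Uninformative capsule, positive half the time.** Expected accuracy as written = t + 0.5(1−t) = 50% + t/2. With 43 patients, 28 correct gives chi-square 6.5²/10.75 = 3.93 (p = 0.047) and 27 gives 2.81 (p = 0.093). The two-sided exact test needs 29 (p = 0.032; 28 gives 0.066).

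| Assumed t | Accuracy | Chance of ≥28 (chi-square) | Chance of ≥29 (exact) |
|---|---|---|---|
| 0% | 50% | 3.3% | 1.6% |
| 10% | 55% | 12% | 7% |
| 20% | 60% | 30% | 20% |
| 30% | 65% | 56% | 44% |

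**5. Uninformative capsule, positive in 58%** (the rate in 2.1), with an assumed 30% of patients above 20 mL. Accuracy as written = t + 0.58·0.30 + 0.42·(0.70−t). At t = 10/20/30% this is 52.6/58.4/64.2%, against 48.4/50.0/51.6% for any blood and 46.8% throughout for >20 mL. The chance of significance is 7/23/52% (chi-square) or 4/15/39% (exact).

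**6. Working capsule.** Assumed: 100% sensitivity above 20 mL, 63% specificity with no blood, 30% of patients above 20 mL, q = 50%.

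| t | As written | Either fixed cut-off |
|---|---|---|
| 0% | 74.1% | 74.1% |
| 10% | 77.8% | 72.8% |
| 20% | 81.5% | 71.5% |
| 30% | 85.2% | 70.2% |

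At t = 20%, cells per 100 patients (TP/FP/TN/FN) and indices are:

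- As written: 40/18.5/41.5/0, sensitivity 100%, specificity 69%.
- >20 mL: 30/28.5/41.5/0, 100% and 59%.
- Any blood: 40/18.5/31.5/10, 80% and 63%.

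If sensitivity above 20 mL were 80% (inside the 54–100% interval in 2.2.5), accuracy at t = 20% is 75.5% as written and 65.5% at either fixed cut-off. With 43 patients, power at a true accuracy of 71.5% is 86% (chi-square) or 78% (exact). At 65.5% it is 59% or 46%.

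**The case against.** The lenience towards capsule-negative patients looks deliberate. Section 4.1 calls 20 mL a detection threshold, Table 3 (section 2.1.3) warns that a negative reading can coexist with highly diluted blood, and 2.2.5 reports earlier accuracy for more than 20 mL. Equally, a capsule that finds 10 mL of real blood has answered the question in the 2.3.3 hypothesis correctly, and a >20 mL reference would call that a false positive. That is a real cost of choosing >20 mL. Each argument supports one fixed reference; neither supports switching between them according to the capsule result.

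The size can also be challenged, and most of that stands.

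- If every small-volume patient is capsule-negative (q = 0), all three indices equal the >20 mL values; if every one is positive (q = 1), they equal the any-blood values. A sharp detection threshold would put q near 0. Over the full range of q at t = 20%, each fixed-cut-off accuracy runs from 61.5% to 81.5%, so 71.5% is a midpoint.
- The 63% specificity (10.5) comes from the multicentre study, described without a volume threshold; the specificity reported with >20 mL is 83% (2.2.5). If that applied to everyone not above 20 mL, t·q could not exceed 0.17 × 0.70, about 12 points. With q = 17% and t = 20% the excess over >20 mL would be 3.4 points, but over any blood it would be 0.20 × 0.83 = 16.6 points.
- An uninformative capsule scores exactly 50% at a fixed cut-off only if it is positive half the time or prevalence is half. At 58% positive and t = 10%, the chance of significance is modest (7% or 4%).

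Finally, 10.4.1 and 10.4.2 can be read as intending a fixed endoscopy status. They give no cut-off and send the reader back to 4.1, so this shows a contradiction in the plan and does not resolve it.

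**Conclusion.** The concern holds. As written, the capsule result chooses the endoscopic cut-off, and a patient with fresh blood or hematin not above 20 mL is never an error. Accuracy exceeds at least one fixed-cut-off value whenever such patients occur; sensitivity and specificity are never lowered and are usually raised. Sensitivity against >20 mL is unchanged when there are no false negatives, and specificity against any blood when there are no false positives. The indices also coincide with one of the two references at q = 0 or q = 1.

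The size depends on t and q, which the documents do not give, and there is no bias if t = 0. The plan does provide a category below 20 mL, so it allows for such patients. The significance probabilities further assume that the test compares correct with incorrect against 50%, and the working-capsule figures are illustrations. Because the fault lies in the definition of the primary endpoint, it must be corrected before results are read.

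**What to change.** Define endoscopy-positive once, independently of the capsule result, and use that definition in all four cells. The sponsor should pre-specify and justify the primary reference: either any fresh blood or hematin, which fits the hypothesis in 2.3.3, or >20 mL, which is the plan's detection threshold. Report the other as a sensitivity analysis, and show small-volume patients as a separate row by capsule result. Align the synopsis, 4.1 and 10.4.2.

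Re-check the 75% planning accuracy and the stated power against the chosen reference, since the multicentre study behind them is described without a 20 mL threshold. While editing, assign exactly 20 mL to a category and apply the 20-minute condition in the same way to all four cells.

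The cost is wording. No new data are needed, because blinded volume grading from the images is already planned (6.3.2, 10.6.1). The downside is that reported accuracy may be less favourable and the power may have to be restated.
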